### **Statistical Analysis Plan**

Baseline categorical variables were described as absolute and relative frequencies, while baseline quantitative variables were expressed as mean and standard deviation (SD). Subjects were analyzed according to their randomization group, regardless of treatment they received. Paired Student's T test was used to compare the primary outcome between the two interventions. For secondary outcomes, categorical outcomes were assessed using the McNemar's test, symmetrical continuous outcomes were assessed using the Paired Student 's T test, and asymmetrical continuous outcomes were assessed using the Wilcoxon's signed-rank test. A significance level of 5% was set for all analyses.

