## **Methods**

### **Study design**

The present study was designed to be an open label, randomized, crossover, two-center, clinical trial aimed to assess the impact of different verticalization positions on lung aeration of patients hospitalized in the ICU under invasive mechanical ventilation using endotracheal tube. Patients were enrolled and followed from the medical-surgical ICUs of Ernesto Dornelles (40 beds) and Moinhos de Vento hospitals (17 beds), both tertiary, academic, and private hospitals, in Southern Brazil.

**Sitting position protocol:** Participants were passively placed in bedside sedestation, where they remained for 30 minutes, with back support; their hips and knees were flexed at 90° and feet supported. This position aimed at simulating sitting in a chair.

**Passive orthostasis protocol:** Participants were transferred to a tilt table (0° inclination). Safety straps were placed on the knees, waist and chest to keep participants in the orthostatic position. The tilt table protocol lasted 30 minutes. Initially, participants were placed in a vertical position up to 45° and remained in this position for 3 minutes. Next, they were tilted to 60°, where they remained for 2 minutes. Then verticalization was performed up to 75-85°, where they remained for another 25 minutes.

**Co-interventions:** Endotracheal aspiration was performed 30 minutes before the beginning of both verticalization position protocols. The critical care management of participants, including IMV parameters were left at the discretion of each center assistant team according to local protocols.

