### **Randomization, washout, and bliding**

Subjects were randomized in an 1:1 ratio to one of two sequences of verticalization protocols: sitting position followed by passive orthostasis or passive orthostasis followed by sitting position. Participants were randomized on the same day they were deemed to be suited to participate in the study. Randomization was performed using blocks of different sizes and stratified by center. Allocation concealment was ensured through the use of a centralized webbased randomization plataform (REDCap, Vanderbilt University, Nashville, TN, USA). Researchers had access to intervention sequence only after the participants were registered on the platform. A washout window period (90 to 150 minutes) in which the patient was returned to bed in supine position (end of the first verticalization protocol) was applied between the two verticalization protocols to avoid the carryover effect. Considering the nature of the trial interventions, blinding was not feasible.

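### The primary paired t-test ignores the randomised order, so any systematic shift between periods widens the confidence interval and costs power that a period-adjusted analysis would recover

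*Combined protocol and SAP*

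**What the plan says.** The Study design section describes an "open label, randomized, crossover, two-center, clinical trial". The section on randomization and washout states that "Subjects were randomized in an 1:1 ratio to one of two sequences of verticalization protocols", the two orders being sitting then orthostasis and the reverse. It adds that "Randomization was performed using blocks of different sizes and stratified by center". A supine washout of 90 to 150 minutes "was applied between the two verticalization protocols to avoid the carryover effect".

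The Statistical Analysis Plan then states that a paired Student's "T test was used to compare the primary outcome between the two interventions". Symmetrical continuous secondary outcomes get the same test, and "asymmetrical continuous outcomes were assessed using the" Wilcoxon signed-rank test. No period or sequence term, period check or sensitivity model is named. The statement that patients are analysed as randomised settles which group each patient belongs to; it does not bring the order into the test.

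**The concern.** In a two-period, two-sequence crossover, position and period are separable only because the order is randomised. The paired t-test pools all orthostasis-minus-sitting differences and does not use the order. A systematic first-to-second-period change therefore stays in the SD of those differences. Blocked 1:1 allocation removes the change from the estimate, but the test takes no credit for this in its standard error.

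The washout is aimed at carryover and does not remove a period shift. A shift is possible here, though not shown. Each position lasts 30 minutes, so the second starts 30 + 90 = 120 to 30 + 150 = 180 minutes after the first starts. Concurrent care is not fixed either: "including IMV parameters were left at the discretion of each center assistant team according to local protocols". Only a systematic shift matters; haphazard changes of settings are noise that no period term can remove.

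At stake are the width of the primary confidence interval and the power of the primary test. If the analysed sequences are unequal in size, the estimate is also biased.

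**Working it through.** **Inputs from the documents.** Two sequences, 1:1, blocked and stratified by centre; paired t-test; 5% significance level (two-sided assumed). The text reviewed gives no sample size, SD, effect size or period shift, so there is no stated figure to reproduce, and those inputs are assumed ranges.

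**Model.** Let tau be the effect of orthostasis minus sitting, delta the systematic period 2 minus period 1 shift, and sigma the within-sequence SD of the within-patient difference. The orthostasis-minus-sitting difference has mean

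- tau + delta when sitting comes first (n_SO patients);
- tau − delta when orthostasis comes first (n_OS patients).

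**Equal sequences.** The mean difference estimates tau without bias, with true SE sigma/√n. The paired t-test estimates its variance as about sigma² + delta², so its SE is too large by k = √(1 + (delta/sigma)²). By normal approximation:

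- type I error = 2(1 − Φ(1.96k));
- power = Φ(1.96 + 0.842 − 1.96k), for an effect with 80% power at delta = 0.

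For example, at delta = 0.5 sigma, k = √1.25 = 1.118 and 1.96k = 2.191. Type I error is 2.8% and power is Φ(0.611) = 73%.

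Simulation at 15 vs 15 (100,000 normal trials per cell) agrees:

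| delta/sigma | k | Paired: type I error | Paired: power | Adjusted: type I error | Adjusted: power |
|---|---|---|---|---|---|
| 0 | 1.000 | 4.9% | 80.3% | 5.0% | 80.2% |
| 0.25 | 1.031 | 4.4% | 78.2% | 5.1% | 80.0% |
| 0.5 | 1.118 | 2.9% | 72.4% | 5.1% | 79.9% |
| 0.75 | 1.250 | 1.5% | 63.0% | 5.1% | 79.8% |
| 1 | 1.414 | 0.6% | 50.2% | 5.0% | 80.1% |

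Paired-test power at n = 20, 40 and 60 is within about 1 point of these values.

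**Unequal sequences.** The paired estimate is off by delta × (n_SO − n_OS)/n. For shifts of 0.25, 0.5 and 1 sigma:

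- 16 vs 14: 2/30 × delta = 0.017, 0.033 and 0.067 sigma;
- 17 vs 13: 4/30 × delta = 0.033, 0.067 and 0.133 sigma.

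Type I error in these cells is 0.9% to 4.6%. With assumed blocks of 2, 4 and 6 in two equally likely centres and n = 30, 10,000 simulated allocations gave exact balance in 58%, 16 vs 14 in 41%, 17 vs 13 in 2%, and nothing larger. Blocking alone therefore does not create false positives. A marked imbalance could: at 24 vs 16, type I error is about 6.3% at 0.5 sigma and 6.4% at 1 sigma, against 5.1% and 5.0% adjusted. Nothing in the documents shows that such losses occurred.

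**Period-adjusted estimate.** The period 2 minus period 1 difference has mean delta + tau when sitting comes first and delta − tau when orthostasis comes first. The sequence means differ by 2 tau, so half that difference estimates tau. Its SE is (sigma/2) × √(1/n_SO + 1/n_OS), on n − 2 degrees of freedom. At 15 vs 15 this is 0.1826 sigma, the same as sigma/√30. At 17 vs 13 it is 0.1842 sigma.

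As a check on the halving, in one simulated 30-patient dataset the half-difference and a linear model with fixed patient, position and period effects both gave −0.163 (SE 0.149, p = 0.284). Unhalved, the figure would be −0.326.

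**Rank tests.** At 15 vs 15, with heavy-tailed symmetric (Laplace) differences and an effect of 0.5 sigma, signed-rank power was 84%, 80%, 72% and 40% at delta = 0, 0.25, 0.5 and 1 sigma. A rank-sum test of period differences gave 81% to 83% throughout.

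**The case against.** The strongest reply is that no defect is shown in this trial. The planned test is valid under the planned design: with blocked allocation the estimate is essentially unbiased and type I error does not exceed 5%. The shift is unknown. At 0.25 sigma the loss is under 2 power points and the interval is 3% too wide; the striking figures belong to 1 sigma, which nothing in the documents supports. Endotracheal aspiration precedes both positions, patients return to supine between them, and both periods fall within a few hours. The primary outcome's measurement is not described in the text reviewed; if it is a change from a pre-position baseline, slow drift would be smaller.

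Most of this stands as a limit on size. The point concerns efficiency, not a false-positive risk, while the sequences stay near-equal. It does not remove the mechanism: aspiration before both positions does not undo a shift due to elapsed time, and blocking protects the estimate but not its standard error.

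The case for changing the rank test is weaker. With skewed differences the rank-sum test showed no gain at 0.25 sigma, about 3 to 5 points at 0.5 sigma, and a loss of at most 3 points with no shift.

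The analysis section is written in the past tense, so the analysis may already be done. That would limit the remedy to an additional analysis.

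**Conclusion.** The concern holds and should be fixed. It is conditional: if a systematic period shift exists and the sequences are near-equal, the primary test is conservative and its interval is 3%, 12% or 41% too wide at 0.25, 0.5 or 1 sigma. The mechanism is certain for this design. The size of the loss in this trial cannot be known from the documents, and it may be negligible. The figures assume normal differences, a two-sided 5% test and an effect with 80% power when there is no shift. The change is justified because the protection costs almost nothing and also removes the bias that would arise if losses before period 2 differed by sequence.

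**What to change.** Make the primary analysis period-adjusted and name this one model. Compute each patient's period 2 minus period 1 difference, compare the two randomised sequences with a two-sample t-test (pooled variance), and report **half** the between-sequence difference, signed as orthostasis minus sitting, with its 95% CI. With complete data this is identical to a linear model with fixed patient, position and period effects, and it uses the same complete-pair patients as the paired test. No centre term is needed: a centre main effect cancels within patients, and centre in a regression of period differences would be a centre-by-period term.

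Use the same approach for symmetrical continuous secondary outcomes. For asymmetrical ones, replace the signed-rank test with a rank-sum test of period differences between sequences. Leave McNemar's test as it is: a sequence-stratified Fisher test on discordant pairs had lower simulated power (64% vs 69% with no period effect; 52% vs 60% with a period log-odds of 1; n = 40).

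If the paired analysis has already been done, keep it as planned and report the period-adjusted result beside it as a declared additional, post hoc analysis.

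The cost is SAP wording, a few lines of code and one degree of freedom, with no new data. With no period effect, simulated power falls by 0.1 points at 15 vs 15 (79.9% to 79.8%), by 0.9 points at 17 vs 13 (80.2% to 79.3%), and by about 2 points for the rank version with Laplace differences (84.1% to 82.1%).

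### The crossover is analysed by a paired t test on complete pairs with no period term, so a period effect inflates the standard error and, if the sequences end up unequal, biases the comparison

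*Combined protocol and SAP*

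**What the plan says.** Under Study design the trial is described this way: "The present study was designed to be an open label, randomized, crossover, two-center, clinical trial". Under the randomisation heading: "Subjects were randomized in an 1:1 ratio to one of two sequences of verticalization protocols". The same section says that randomisation was blocked and stratified by centre, describes the break between periods as "A washout window period (90 to 150 minutes) in which the patient was returned to bed in supine position", and adds: "Considering the nature of the trial interventions, blinding was not feasible".

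The Statistical Analysis Plan is one paragraph. For the primary outcome, the paired Student's "T test was used to compare the primary outcome between the two interventions"; symmetrical continuous secondary outcomes are treated the same way. For the rest: "For secondary outcomes, categorical outcomes were assessed using the McNemar" test, and "asymmetrical continuous outcomes were assessed using the Wilcoxon" signed-rank test. It also states: "Subjects were analyzed according to their randomization group, regardless of treatment they received".

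No period, sequence or centre term is named, and there is no model, no imputation and no rule for a patient measured in one period only.

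**The concern.** In a two-period crossover, each patient's difference between positions contains the period effect, with opposite sign in the two sequences. The paired t test pools these differences as if they had one mean. Two consequences follow.

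- With equal sequences the period effect cancels from the estimate but stays in the spread of the differences. The standard error is overstated, the test is conservative and power is lost.
- With unequal sequences the cancellation is incomplete, and part of the period effect is reported as a position effect.

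The washout is there to prevent carryover. It does not remove a period effect such as a change in the patient's condition or ventilator settings over the session.

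Separately, every named test needs both values, so a patient with one measured period drops out of every comparison. That exclusion comes from the pairing, not from the missing period term: a period-adjusted analysis of differences would drop the same patients. The two issues meet because loss before period 2 is one way in which the sequences become unequal.

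**Working it through.** **Inputs.** From the documents: two sequences, 1:1, paired t test, 5% level (two-sidedness assumed). Not in the documents, so assumed: period effect d (period 2 minus period 1, in SD units of the outcome), within-patient correlation r, number of patients N, loss rates. The plan gives no figure to reproduce.

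**Complete pairs.** Adding 3 one-period patients to 20 simulated pairs left the paired t p-value (0.1776) and the signed-rank p-value (0.2162) unchanged. McNemar's test uses only the discordant pairs, so the same holds there.

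**Standard error.** Take orthostasis minus sitting, with true effect τ. Its mean is τ − d in the orthostasis-first sequence (n_O patients) and τ + d in the sitting-first sequence (n_S). The SD of the within-patient difference is s = √(2(1 − r)). The paired t test overstates its standard error by about √(1 + (4·n_O·n_S/N²)·(d/s)²).

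For r = 0.5, s = 1. With equal sequences, large-sample type I error is 2(1 − Φ(1.96 × factor)):

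| d (SD) | SE factor | Type I error |
|---|---|---|
| 0.1 | 1.005 | 4.9% |
| 0.2 | 1.020 | 4.6% |
| 0.3 | 1.044 | 4.1% |
| 0.5 | 1.118 | 2.8% |

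Simulation at N = 30 and d = 0.3 gave about 4.2%. At r = 0.8, s = √0.4 = 0.632, so d = 0.3 gives √(1 + 0.225) = 1.107 and about 3.0%.

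**Power.** N = 30, r = 0.5, d = 0.3, and an assumed position effect of 0.51 SD:
- Adjusted: SE = 1/√30 = 0.1826, 28 df, critical value 2.048. Power ≈ Φ(0.51/0.1826 − 2.048) = Φ(0.745) = 77%.
- Paired t: SE = 0.1826 × 1.044 = 0.1906, 29 df, critical value 2.045. Power ≈ Φ(0.51/0.1906 − 2.045) = Φ(0.631) = 74%.

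**Bias from unequal sequences.** The paired mean estimates τ + d(n_S − n_O)/(n_S + n_O). With 15 per sequence and random loss of 20% (orthostasis-first) versus 5%, 12 and 14.25 pairs remain on average. The bias is 0.3 × 2.25/26.25 = 0.0257 SD. The standard error is about 1/√26.25 = 0.195, so this is about 0.13 of a standard error. Type I error in simulation was 4.4%, so it was not inflated.

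**Period-adjusted estimate.** Average the two sequence means: [(τ − d) + (τ + d)]/2 = τ, whatever n_O and n_S. In simulation the bias fell from 0.028 to 0.002 SD. With 12 and 14.25 pairs, its SE is larger by √(26.25²/(4 × 12 × 14.25)) = 1.004.

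**Keeping one-period patients by a mixed model.** Bias in SD units with no true effect, no period effect and r = 0.5. Loss takes the worst values of the named quantity; rates are orthostasis-first versus sitting-first:

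| Loss depends on | Loss | Complete pairs | Mixed model |
|---|---|---|---|
| Observed period-1 value | 20% vs 5% | 0.0505 | about 0 |
| Same, but random in sitting-first | 20% each | 0.0875 | about 0 |
| Patient's stable level | 20% vs 5% | 0 | −0.049 |
| Same, but random in sitting-first | 20% each | about 0 | −0.066 |
| Unseen period-2 value | 20% vs 5% | −0.051 | −0.093 |

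Period adjustment does not cure loss that depends on response. With λ(p) = φ(z_p)/(1 − p), λ(0.20) = 0.350 and λ(0.05) = 0.109, the first row becomes (1 − r)(0.350 − 0.109)/2 = 0.060 instead of 0.0505.

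**The case against.** The strongest reply is that little may be at stake. The two 30-minute protocols and the 90 to 150 minute washout together span 150 to 210 minutes, so both loss and drift may be small. Endotracheal aspiration is timed identically before each position. Blocked 1:1 allocation keeps the sequences nearly equal at entry, and a period effect then makes the test conservative, not anti-conservative. All of this stands and limits the priority. It does not justify leaving the term out, since adjustment costs almost nothing and ventilator management was left to each centre's team.

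A reader might infer four stronger things that the documents do not support.

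- *That the paired test gives false positives.* A period effect alone lowers its type I error. Inflation in the illustrations needed loss tied to response, up to 9.5% at 60 patients with 20% loss in each sequence by different mechanisms.
- *That loss depended on sequence.* The lack of blinding makes this possible; nothing shows that it happened.
- *That the plan breaks its own statement on analysis by randomised group.* That sentence governs how patients are classified and is silent on missing outcomes.
- *That one-period patients should enter the primary analysis through a mixed model.* The model corrects loss that follows the observed period-1 value. It adds bias when loss follows the patient's stable level, where the paired difference is unbiased, and has the larger bias when loss follows the unseen period-2 value. The documents favour none of these mechanisms.

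**Conclusion.** The concern holds for the missing period term. Any period effect overstates the standard error of the paired t test, and it biases the position effect if the sequences end up unequal. At d = 0.3 SD, r = 0.5 and 30 patients, the cost is a type I error of about 4.1 to 4.2% and about 3 points of power. With 20% versus 5% random loss the bias is about 0.026 SD. These figures rest entirely on assumed inputs, and with no period effect both problems vanish.

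The exclusion of one-period patients is a fact of the named tests, but it is not shown to cause bias here, and including them is a trade-off. Priority is low to moderate.

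**What to change.** - **Primary and other continuous outcomes:** analyse with position and period terms and patient effects. This is equivalent to comparing the period differences between the two sequences. For a skewed outcome, use a transformed scale named in advance.
- **If outcome data have already been seen** (the documents are written in the past tense): keep the paired test primary and report the period-adjusted result beside it.
- **Sensitivity analysis only:** a REML mixed model with Kenward-Roger standard errors and degrees of freedom that includes one-period patients, with its missing-at-random assumption stated. A normal reference should not be used: its type I error reached 6.4% at 30 patients (20% versus 5% loss, correlation 0.5).
- **Categorical outcomes:** keep McNemar's test and add event counts by position and period.
- **Reporting:** state how a missing period is handled, and report incomplete patients by sequence and reason. If none were incomplete, one sentence settles that part.

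The cost is SAP wording, one adjusted analysis and one sensitivity model per continuous outcome, and one degree of freedom. At 30 patients the critical value moves from 2.045 to 2.048.

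### Does choosing between the paired t-test and the Wilcoxon test by symmetry of the outcome, with no Wilcoxon hypothesis stated, undermine the secondary analyses?

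*Combined protocol and SAP*

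**What the plan says.** The Study design section describes an "open label, randomized, crossover, two-center, clinical trial". Under Randomization, washout, and bliding, "Subjects were randomized in an 1:1 ratio to one of two sequences of verticalization protocols". Each patient with both periods therefore gives one difference between sitting and orthostasis per outcome.

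In the Statistical Analysis Plan the primary test is fixed: the paired Student's "T test was used to compare the primary outcome between the two interventions". For secondary outcomes the choice depends on shape: "symmetrical continuous outcomes were assessed using the Paired Student" test, "and asymmetrical continuous outcomes were assessed using the Wilcoxon" signed-rank test. Then: "A significance level of 5% was set for all analyses".

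The section does not say whether symmetry is judged on the outcome or on the difference, or by what criterion. It attaches no hypothesis, estimate or interval to the Wilcoxon test. It attaches no estimate or interval to the paired t-test or McNemar's test either.

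**The concern.** Both candidate tests depend on the data only through within-patient differences, so a rule that looks at the outcome looks at the wrong quantity. The two shapes can disagree in either direction. With an assumed N of 30 and a cut-off of |sample skewness| > 1:

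- Skewed patient levels with normal within-patient error: the outcome is flagged in 67% of samples, the differences in 2.5%.
- Normal patient levels with an exponential response to one position: the outcome is flagged in 3.4%, the differences in 62%.

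Two careful analysts could therefore pick different tests from the same text. In addition, when differences are skewed the signed-rank test is not in general a 5% test of a zero mean or zero median. A significant result might then be reported as a mean or median difference that the test does not establish. What is at stake is the reproducibility and reading of secondary results.

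**Working it through.** The plan gives no figure to reproduce. The visible text states no sample size, SD or distribution, so every N and shape below is an assumption. Tests are taken as two-sided at 5%; the plan states 5% but not sidedness.

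**1. What randomisation guarantees.** Let p_i be patient i's period 1 minus period 2 difference, and d_i the sitting minus orthostasis difference. If position has no effect, p_i does not depend on sequence, and d_i = s_i × p_i, where s_i is +1 or −1 with probability 1/2 each. So d_i is symmetric about zero whatever the distribution of the outcome, which is the condition the signed-rank test needs.

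Simulation agrees. With a lognormal outcome (log-scale SDs 0.7 between and 0.5 within patients), balanced sequences and no period effect, it rejects 4.2% to 5.2% for N = 12 to 100. With a period effect of 0.5 on the log scale it rejects below 2%, an error on the conservative side.

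**2. Cost of judging the outcome instead of the difference.** Take a lognormal patient level plus normal within-patient error of SD 1. The outcome has skewness of about 4.8 and the difference about 0, so the plan's wording sends it to Wilcoxon. The power columns use a shift of 0.6, which is 0.6/√(1 + 1) = 0.42 SD of the difference.

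| n | Level, Wilcoxon | Level, t | Power, Wilcoxon | Power, t |
|---|---|---|---|---|
| 20 | 5.0% | 5.1% | 0.42 | 0.44 |
| 40 | 4.7% | 4.8% | 0.72 | 0.74 |
| 60 | 5.1% | 5.2% | 0.88 | 0.90 |
| 100 | 5.1% | 4.9% | 0.99 | 0.99 |

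With 10,000 samples the simulation error at 5% is √(0.05 × 0.95/10,000) = 0.22 points. The levels are indistinguishable and the power loss is at most about two points.

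**3. Where the large rates come from.** Give the differences a shifted exponential shape (skewness 2), with true mean or true median zero.

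| n | Wilcoxon, mean 0 | t, mean 0 | Wilcoxon, median 0 |
|---|---|---|---|
| 20 | 12.6% | 8.3% | 9.9% |
| 40 | 19.9% | 7.2% | 17.6% |
| 60 | 25.9% | 6.4% | 24.5% |
| 100 | 37.8% | 5.8% | 38.2% |

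The t column also covers the opposite mismatch, a symmetric outcome with skewed differences sent to the t-test: 8.3% falling to 5.8%.

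With milder skewness the Wilcoxon rates for zero mean at N = 20/30/40/60 are:

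- skewness 0.5: 5.2/5.9/5.8/6.1%
- skewness 1: 6.5/7.7/8.3/9.9%

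By step 1, skewed differences cannot arise if position has no effect. In these settings position does change patients' values, so the rejections are correct for the null that randomisation supports. They are errors only against a zero-mean or zero-median hypothesis, which the plan does not state.

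**4. Would a stated estimate settle it?** The usual companion to Wilcoxon is the Hodges-Lehmann estimate, which targets the median of the average of two differences. For a standard exponential this is the m solving e^(−2m)(1 + 2m) = 0.5, so m = 0.839 (check: e^(−1.678) × 2.678 = 0.50). The mean is 1 and the median ln 2 = 0.693. The estimate thus sits 0.839 − 1 = −0.161 from the mean and 0.839 − 0.693 = +0.146 from the median. Where the differences are skewed it measures neither, so prescribing it would not remove the ambiguity.

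**The case for a change.** The strongest case for a change is that it would be cheap: two or three sentences could define symmetry on the differences, assign a test to each outcome and state the Wilcoxon hypothesis. The choice of test cannot be reproduced from the visible text, and that stands. A free choice also lets an analyst take the smaller p-value. The false-positive rate is then at most 5% + 5% = 10% per outcome, and well below that in practice because the two tests use the same differences and are strongly correlated.

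The rest is weaker. Reading the rule as symmetry of the differences is natural in a sentence that names only paired tests, but it sends to Wilcoxon exactly the outcomes for which it is not a mean or median test. Redefining symmetry that way would therefore not cure the interpretation problem. The missing estimate is a general feature of the section and not specific to Wilcoxon. The lack of a test for each named outcome cannot be held against the plan, because the visible text lists no secondary outcomes and part of the document was removed.

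**Conclusion.** No change follows. Applied as written, the rule gives secondary tests that hold about 5% for no effect of position, and the cost of classifying by the outcome is about two points of power or less. The high rejection rates need two things together: marked skewness of the differences, and a claim about the mean or median that the plan does not make. The gap is real but small: an unstated criterion for secondary continuous outcomes, which analysts can fill by looking at the paired differences and by reading a significant signed-rank result as evidence of some effect of position unless those differences are reasonably symmetric.

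This rests on the 1:1 randomised sequence stated in the protocol, on two-sided 5% tests, and on assumed sample sizes of 12 to 100 and assumed shapes. The validity argument in step 1 of the working does not depend on the shapes; the power comparison does.
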